## 5.2 Early Study Termination

The Study may be terminated early at the discretion of the Sponsor, if there is sufficiently reasonable cause. In the event of such action, written notification documenting the reason for Study termination will be provided to each Investigator.

Circumstances that may warrant early termination include, but are not limited to:

- Determination of unexpected, significant, or unacceptable risk to patients;
- Other administrative reasons.

Should the Study be terminated prematurely, all Study materials must be returned to the Sponsor or Sponsor's designee.

## 5.3 Dose and Administration

Avapritinib will be administered PO at the dose received by the patient on the prior avapritinib protocol in continuous 28-day cycles. Dosing will be continuous, with no inter-cycle rest periods unless warranted for individual safety reasons. Pre-specified dose modification recommendations for AEs related to avapritinib are described in [Section 5.3.1](#).

Avapritinib should be administered with a glass of water (at least 8 ounces or 250 mL). The tablets should be taken on an empty stomach at least 1 hour before or least 2 hours after a meal. Each dose should be administered at approximately the same time each day. Do not make up for a missed dose within 8 hours of the next scheduled dose. If a patient vomits during or after taking avapritinib, the dose should not be replaced, and the next dose should be taken at the next scheduled dosing time.

Patients should be instructed to swallow tablets whole and to not chew the tablets. Interruption in avapritinib dosing may be required for surgery or other procedure during the treatment period. At a minimum, avapritinib should be discontinued 48 hours before the procedure and resumed 48 hours after the procedure is completed.

### 5.3.1 Dose Reduction for Adverse Events

Dosing modifications are recommended for patients experiencing avapritinib-related toxicity. Modification guidelines are summarized in [Table 2](#).

If a patient experiences a Grade 3 or worse (based on NCI CTCAE criteria) AE thought to be caused by avapritinib, avapritinib treatment should be interrupted until the AE improves to Grade 2 or to the patient's baseline, or it is considered stable, and does not preclude continued therapy. At that time, avapritinib treatment may resume either at the same dose, or at reduced dose. Dose reductions should be in increments of 100 mg. If a Grade 3 or worse AE recurs, dosing should be interrupted as described above, and if dosing is resumed, the dose should be reduced by at least 100 mg.

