**Table 2: Dose Modification Guidelines for Avapritinib-related Toxicity**

Toxicity	Modification
General	
Grade 1 or Grade 2	
 
• No dose modification required
 

Grade 3 - 4	
 
• Occurrence: Hold until event is <math>\leq</math> Grade 2, or has returned to baseline, and then resume by reducing the dose by 100 mg less than the current dose 
 
◦
 
 
 
• Occurrence at 100 mg: Discontinue avapritinib 
 
◦
 
 
 

Cognitive or Mood Effects	
Grade 1 with only minor impairment	No dose modification required
Grade 1, other than minor impairment	
 
• Interrupt dosing for 7 days, and resume dosing without dose reduction
 
• The dosing interruption may be repeated if the impairment continues to worsen after resuming dosing; however, repeated dosing interruption is at the discretion of the investigator, and should be balanced with the need to treat the underlying GIST
 

Grade 2	
 
• Interrupt dosing for a minimum of 7 days
 
• Resume dosing with a dose reduction of 100 mg when the cognitive effect has improved to Grade 1 or less, or still at Grade 2, if continued treatment is considered in the best medical interest of the patient due to the underlying GIST
 
• If the patient is already receiving a dose of 100 mg QD, and continued treatment is considered in the best medical interest of the patient due to the underlying GIST, treatment may be resumed at 100 mg
 

Grade 3-4	
 
• Interrupt dosing for a minimum of 14 days
 
• Resume dosing with a dose reduction of 100 mg when the cognitive effect has improved to Grade 1 or less, or when it has improved to Grade 2, if continued treatment is considered in the best medical interest of the patient due to the underlying GIST
 
• Occurrence at 100 mg: Discontinue avapritinib
 

Intracranial Bleeding	
Grade 1-4	
 
• Discontinue avapritinib
 

Abbreviations: CNS = central nervous system; GIST = gastrointestinal stromal tumor; QD = once daily.

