 Changes in cognition, memory, attention, mood, or speech (thought to originate in the CNS). If avapritinib treatment is resumed after interruption for a cognitive or mood effect, or for an intracranial bleeding event, the investigator must document in writing that resuming avapritinib treatment was considered to be in the best medical interest of the patient.

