### **9.3 Documenting Serious Adverse Events and Adverse Events of Special Interest**

Each patient must be carefully monitored for the development of any SAEs and AESIs, Adverse Events of Special Interest for avapritinib are, regardless of grade or causality:

- cognitive effects which include the following terms: memory impairment, cognitive disorder, confusional state and encephalopathy.
- intracranial bleeding including haemorrhage intracranial, cerebral haemorrhage, and subdural haematoma.

This information should be obtained in the form of non-leading questions (eg, “How are you feeling?”) and from signs and symptoms detected during each examination, observations of study personnel, and spontaneous reports from patients.

All SAEs and AESIs reported by the patient or revealed by observation, physical examination, laboratory testing or other diagnostic procedures will be recorded in the appropriate section of the CRF. When possible, signs and symptoms indicating a common underlying pathology should be noted as one comprehensive event.

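### Section 5.3.1 and Table 2 disagree on a first drug-related Grade 3-4 event, and give opposite instructions at 100 mg and for intracranial bleeding

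*Combined protocol and SAP*

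**What the plan says.** Section 5.3.1 recommends dose modifications for avapritinib-related toxicity and refers to Table 2 as the summary of those guidelines. Its text covers every related event of Grade 3 or worse, with no exception by dose level or type of event. Treatment is interrupted until the event reaches Grade 2 or baseline, "or it is considered stable, and does not preclude continued therapy". The section continues: "At that time, avapritinib treatment may resume either at the same dose, or at reduced dose". Only when such an event recurs does it call for a reduction, of 100 mg or more, if dosing resumes.

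Table 2 has three blocks that bear on this:

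- **General, Grade 3-4.** Hold until the event is no worse than "Grade 2, or has returned to baseline, and then resume by reducing the dose by 100 mg less than the current dose". A second bullet reads "Occurrence at 100 mg: Discontinue avapritinib". First and later events are not distinguished.
- **Cognitive or mood effects, Grade 3-4.** "Interrupt dosing for a minimum of 14 days", then resume 100 mg lower once the event is at Grade 1 or less, or at Grade 2 if continuing is judged to be in the patient's interest. An event at 100 mg again leads to discontinuation.
- **Intracranial bleeding, Grade 1-4.** "Discontinue avapritinib", with nothing further.

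Footnote 2 is attached to both the cognitive and the bleeding headings. It begins "If avapritinib treatment is resumed after interruption for a cognitive or mood effect, or for an intracranial bleeding event", and requires the investigator to document why resuming was justified.

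**The concern.** A summary table and the text it summarises should lead a site to the same action. Here an investigator facing a first severe drug-related event can follow the protocol and arrive at different doses, or at continuing rather than stopping.

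The conflicts fall where they matter most. Section 9.3 names cognitive effects and "intracranial bleeding including haemorrhage intracranial, cerebral haemorrhage, and subdural haematoma" as the adverse events of special interest, and the second objective in Section 2 is to characterise the rates of these and of serious adverse events. Section 5.5 acknowledges that intracranial bleeding has occurred in treated patients. Two sites could manage the same bleed in opposite ways, each with protocol text in support.

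There is also a smaller effect on reporting. Section 10 plans descriptive summaries of treatment duration and of reasons for stopping treatment, and the Protocol Summary adds discontinuation itself. With conflicting rules, these outputs partly reflect which text a site happened to follow.

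**Working it through.** There is no sample size, power or test behind this point, so the check is a comparison of texts plus the arithmetic of the 100 mg step.

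**Inputs.** The maximum dose is 300 mg once daily (Section 3.1), the tablet strength is 100 mg (Section 7.1.1.1), a cycle is 28 days (Sections 3.1 and 5.3), and about 5 patients are expected (Section 4.1). The dose levels 300, 200 and 100 mg follow from the cap and the tablet strength. The documents do not say which doses patients will bring with them.

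**First related Grade 3-4 event**

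| Situation | Section 5.3.1 | Table 2 | Both satisfiable? |
|---|---|---|---|
| General, at 300 mg | 300 mg or reduced | 200 mg | Yes, if reduced by 100 mg after improvement |
| General, at 200 mg | 200 mg or reduced | 100 mg | Yes, if reduced by 100 mg after improvement |
| General, at 100 mg | May resume | Discontinue | Not if treatment resumes |
| General, event stable but still above Grade 2 and baseline | May resume | No route to resume | Not if treatment resumes |
| Cognitive or mood | No minimum interruption; same or reduced dose | At least 14 days; 100 mg lower; discontinue at 100 mg | Above 100 mg, by following the table |
| Intracranial bleeding, any dose | May resume | Discontinue | Not if treatment resumes |

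**Size of the dose difference when the same-dose option is used**

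- From 300 mg: (300 − 200)/300 = 33% lower under Table 2.
- From 200 mg: (200 − 100)/200 = 50% lower under Table 2.
- If the site instead chooses the 100 mg reduction that Section 5.3.1 also allows, both differences are 0%.

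**Recurrence.** A reduction of 100 mg or more from 100 mg leaves 100 − 100 = 0 mg, which matches discontinuation in Table 2. The contradiction at 100 mg therefore concerns the first event.

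**Cognitive or mood row.** The minimum interruption is 14/28 = 50% of a cycle; Section 5.3.1 states none.

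**Intracranial bleeding.** Two conflicts overlap. Section 5.3.1 against the table row concerns related events of Grade 3-4, because the section starts at Grade 3. Footnote 2 against the row concerns Grades 1-4 and remains even if Section 5.3.1 is set aside.

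**Could another passage settle it?**

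- No order of precedence is stated, and Section 5.3.1 does not describe Table 2 as an exception to its text.
- Section 5.3 uses discontinuation for a temporary stop around procedures. Table 2, however, uses separate words for holding or interrupting and for discontinuing, so a temporary meaning does not fit there.
- Section 4.6 lists adverse events only among the optional reasons for withdrawal, and bleeding is not among the mandatory ones.

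**Reporting.** One patient in about 5 is 1/5 = 20 percentage points.

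**The case against.** The strongest counter-argument is that Section 5.3.1 only permits resumption. A site that discontinues at 100 mg, or after a bleed, breaches neither text. The condition that the event must not rule out further therapy could also be read as governing every route back to treatment, with the table's discontinuation entries naming the events that do rule it out. Specific rows commonly supplement general text, and footnote 2 is conditional: it can be read as documenting a departure from guidelines that are only recommended.

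Part of this stands. The cognitive row's 14-day minimum is mostly added detail, and above 100 mg a site can generally meet both texts by following that row. The bleeding conflict with Section 5.3.1 is limited to events attributed to avapritinib. The General row in the available copy shows empty sub-bullets, so wording may have been lost there in reading the PDF. The 20-point figure is simply one patient in five and would apply to any yes/no item in this study.

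The core remains. A permission to resume and an instruction to stop cannot both guide an investigator who is deciding whether to resume. The wider reading of the condition is possible, but the protocol does not state it, and it does not explain why a footnote on the bleeding heading provides for resumption. The empty sub-bullets do not touch the bleeding row or the footnote.

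**Conclusion.** The concern holds and must be fixed. For a first related Grade 3-4 event the texts are inconsistent at 200 and 300 mg, with a difference in resumed dose from 0% up to 50% or 33% respectively. They give opposite directions at 100 mg and for related Grade 3-4 intracranial bleeding at every dose. Footnote 2 also conflicts with its own table row for bleeding of any grade from 1 to 4. At recurrence the texts largely agree.

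This rests on the current wording and on dose levels of 100, 200 and 300 mg. The documents give no frequency for these events in the patients who will roll over, so how often the conflict would arise is unknown. Patient safety is the main issue; the effect on the descriptive summaries is secondary.

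**What to change.** Reconcile Section 5.3.1, Table 2 and footnote 2 on five points:

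1. handling of a first event as distinct from a recurrence;
2. the condition for resuming, including whether a stable event qualifies;
3. an event in a patient already at 100 mg;
4. whether the Grade 3-4 cognitive or mood row replaces or adds to the general text;
5. the intracranial bleeding row and the footnote wording on resuming after such an event.

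Which version applies is for the sponsor's clinical team to decide; no dose or rule is proposed here. A sentence saying which text governs if they differ would prevent a repeat.

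A minor point for the same amendment: the 300 mg maximum appears in Section 3.1 but not in the dosing text of the Protocol Summary or Section 5.3. This matters only if a patient enters above 300 mg, which the documents do not establish, but the three statements should match.

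The cost is wording changes in one amendment. Sample size and planned analyses are unaffected.

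### After a first general Grade 3-4 drug-related event, Section 5.3.1 and the Table 2 row said to summarize it recommend different restart rules

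*Combined protocol and SAP*

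**What the plan says.** Section 5.3 (Dose and Administration) sends the reader to Section 5.3.1: "Pre-specified dose modification recommendations for AEs related to avapritinib are described in" that section. Section 5.3.1 opens with "Dosing modifications are recommended for patients experiencing avapritinib-related toxicity" and continues "Modification guidelines are summarized in" Table 2. The text and the table are therefore presented as one set of guidance, advisory in force.

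The second paragraph of Section 5.3.1 is triggered as follows: "If a patient experiences a Grade 3 or worse (based on NCI CTCAE criteria) AE thought to be caused by avapritinib". Dosing is interrupted until the event has eased to Grade 2 or baseline, and the text adds a further alternative: "or it is considered stable, and does not preclude continued therapy". The restart rule that follows is "At that time, avapritinib treatment may resume either at the same dose, or at reduced dose". A reduction is called for only when such an event comes back. Dosing is then held on the same terms, and any restart is to be lower: "if dosing is resumed, the dose should be reduced by at least 100 mg".

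The General row of Table 2 for Grade 3-4 events has two visible instructions. The first is to hold until Grade 2 or lower, or baseline, and then restart at the current dose minus 100 mg. The second is to discontinue if the event occurs on 100 mg. Cognitive or mood effects and intracranial bleeding have separate rows.

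**The concern.** A table that summarizes a section should not give a different answer from that section. Here the answers differ for the patient who has just had a severe event attributed to the drug. A site working from the text could return the patient to full dose, or restart with the event still at Grade 3. A site working from the table would do neither.

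The written rule carries much of the safety load in this study. After Cycle 1 Day 1, scheduled visits are three months apart (Table 1). Monitoring is routinely by phone or email (Section 12). Section 6.2.5 has adverse events recorded locally, with only serious ones going to the sponsor. A non-serious Grade 3 event restarted at the same dose might therefore never be questioned centrally. At entry the protocol is tighter: exclusion criterion 3 delays treatment for Grade 3 or higher events until Grade 2 or baseline, unless the sponsor approves the start. Section 5.3.1 asks for no such approval before a restart with a stable event.

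What is at stake is consistent handling of severe toxicity and, for a patient on 100 mg, whether that patient appears as discontinued or as continuing.

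**Working it through.** The plan gives no figure on this point, so the check is a comparison of the two texts followed by a small calculation.

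**Available doses.** Tablets are 100 mg (Section 7.1.1.1) and are swallowed whole (Section 5.3). The maximum is 300 mg once daily (Section 3.1). The possible doses are therefore 100, 200 and 300 mg, with no step between 100 mg and stopping.

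**First general Grade 3-4 related event, side by side.**

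| Situation | Section 5.3.1 permits | Table 2, General row (visible text) |
|---|---|---|
| On 300 mg, event resolved to Grade 2 | 300 mg, or a reduced dose | 200 mg |
| On 200 mg, event resolved to Grade 2 | 200 mg, or 100 mg | 100 mg |
| On 100 mg | 100 mg (by inference: same-dose clause, no exception stated) | Discontinue |
| Still Grade 3, stable, treatment not precluded | Restart | Stay on hold, unless Grade 3 is the patient's baseline |

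The same-dose and stable-event differences are explicit. The 100 mg difference is inferred.

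**Recurrence.** The dose rules then largely agree: at least 100 mg lower, which from 100 mg leaves no dose. The stable-event difference persists, because Section 5.3.1 carries its interruption rule forward.

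**Is the row just shorthand?** Probably not. Where Table 2 intends a restart without reduction it says so (cognitive or mood, Grade 1 beyond minor impairment). Where it intends a restart at 100 mg it also says so (cognitive or mood, Grade 2). The General row is not limited to second occurrences. It does contain two empty sub-bullets in the text available, so this comparison rests on what is visible.

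**Effect on planned outputs.** Section 10 reports reasons for discontinuation and describes treatment duration. With about 5 patients (Section 4.1), one patient is 1/5 = 20% of the Safety Population. Dose level is not a listed output. A hold is not a discontinuation, and Section 10 does not say whether duration excludes interruptions, so the effect of the stable-event difference on the summaries is uncertain.

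**How often could the 100 mg case arise?** The documents do not give the number of patients on 100 mg, m, or the chance of a first qualifying event, r. As assumptions only, take m = 0, 1 or 2 and r = 0.10 to 0.30. The chance of at least one qualifying event among patients on 100 mg is 1 - (1 - r)^m:

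- m = 0: 0
- m = 1: 0.10 to 0.30
- m = 2: 1 - 0.9² = 0.19 to 1 - 0.7² = 0.51

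These are chances of an event. Management differs only if the site also relies on Section 5.3.1 over the table's instruction to stop, and there is no basis for putting a probability on that. The figures are therefore upper bounds under the assumed inputs.

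**The case against.** The strongest reply is that no site is forced to break anything. Both texts are recommendations, Section 5.3.1 is permissive, and a site that follows Table 2 complies with both at every dose. Investigators may also withdraw a patient for any adverse event (Section 4.6). This stands, and it limits the severity. It does not remove the difference: the reverse does not hold, and no section says which text governs.

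A second reply is that Section 5.3.1 never mentions a patient on 100 mg, so the specific stop rule in the table fills the gap. That is a reasonable reading. A reader might infer that Section 5.3.1 expressly authorizes restart for such a patient; it does not. Nor is restarting at 100 mg in itself a departure, since Table 2 sends a patient on 200 mg there. Only the patient already on 100 mg is at issue.

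A third reply is that the restart with a stable event is not open-ended, because the event must also leave continued treatment possible. That condition is a real safeguard, but the visible table row has no counterpart to the option at all.

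A reader might also infer that Section 5.3.1 allows same-dose restarts without limit. That would require recurrence to mean only the same event returning, and every new severe event to be a different one. The text does not settle what counts as a recurrence, so this cannot be asserted.

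Finally, nothing shows that the sponsor intended the stricter rule. These patients are judged to be benefiting (Section 4.3), and Section 1.1.3 describes a lack of standard alternatives. The choice of direction is the sponsor's.

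**Conclusion.** The inconsistency is real in the current text and is a minor safety-wording correction. For a first general Grade 3-4 related event, the two places differ explicitly on restart dose and restart condition, and by inference on the patient already on 100 mg. The first two differences also apply at 200 and 300 mg.

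The countable effect is 20 percentage points of the discontinuation summary per affected patient on 100 mg, assuming 5 patients; the number on that dose may be zero. The 10% to 51% range for one or two such patients depends on assumed inputs. A reader might take it as the chance that care changes, but it only bounds that chance from above. Nor should a reader infer harm to the study's conclusions: sample size rests on expected rollover and the planned summaries are descriptive, so no test, interval or error rate is touched.

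**What to change.** Make the two texts agree on restart dose, restart condition and the rule at 100 mg, in one of two ways:

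- **Align the text with the table.** Rewrite the second paragraph of Section 5.3.1 so that general Grade 3-4 related events are held to Grade 2 or lower or baseline, restarted 100 mg lower, and lead to discontinuation if they occur on 100 mg.
- **Align the table with the text.** If discretion to restart at the same dose or with a stable event is wanted, write it into the General row, with a definition of recurrence and an explicit rule for 100 mg.

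In the same edit, state that cognitive or mood effects and intracranial bleeding follow their own Table 2 rows. The paragraph now covers any related event of Grade 3 or worse, while the table asks for at least 14 days off drug for Grade 3-4 cognitive or mood effects and discontinuation for intracranial bleeding. Also remove from footnote 2 of Table 2 the reference to resuming after intracranial bleeding, since that row says to discontinue.

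The cost is one paragraph or one table row plus these two small edits in an amendment, and a notice to sites. No visits, procedures or patients are added. The first option takes away some investigator discretion in patients who are benefiting; the second takes away none.
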